## Study Overview

**Anticipated end date for collecting data:** 2025-06-30

**Anticipated end date for analyzing data:** 2025-08-31

**Is this research funded? Yes**

**Funding Source(s):** Federal government

**Supply all Agency Grant Numbers & Titles currently associated with this protocol:**

National Institutes of Health  
NATIONAL INSTITUTE ON ALCOHOL ABUSE AND ALCOHOLISM  
Award Number 5R61AA030581-02  
Unique Federal Award Identification Number (FAIN) R61AA030581

**Do any of the Funding Sources create a Conflict Of Interest for the Principal Investigator, Faculty Sponsor or Research Team (Sub-Investigators) listed on this protocol? No**

**What is the purpose in conducting this research?** How does this study contribute to the advancement of knowledge and why is it worth doing?

Alcohol exposed pregnancy (AEP) can result in Fetal Alcohol Spectrum Disorders (FASDs) that cause lifelong costly disabilities from brain, organ, tissue, and neurological damage. While over 3.3 million US women per month are at risk for AEP, risk for AEP among Native American (Native) women is higher, due to low contraception use and high binge drinking rates. For example, 20% of sexually active Native women in the Southwestern US are at risk for AEP, and 52% of pregnancies in the Navajo Nation are unplanned, compared to 45% nationally. Among Native pregnant women from Great Plains tribes, nearly 30% drink at binge levels and do not use birth control to prevent pregnancy. Among another sample of Native women from Great Plains tribes, 65% were sexually active, not seeking pregnancy, and not using birth control.

AEP can be prevented by avoiding an unintended pregnancy or reducing alcohol intake by those who may become pregnant. MPI [name] was a PI on the seminal CHOICES study that developed the first efficacious theory-based AEP intervention, with 4 Motivational Interviewing (MI) counseling sessions. MPI [name] adapted CHOICES for Native women in tribal communities. The

Native-adapted CHOICES reduced AEP risks among Native women, but was too costly to sustain for high-risk women and communities. In contrast, theory-based digital interventions are highly accessible, more convenient, scalable, and more sustainable, while still efficacious. In R34AA020853, [name] piloted the first automated digital AEP intervention, CARRII. A nationwide pilot RCT showed that CARRII (but not the education control) significantly reduced AEP risk and pregnancy risk at 3 and 6 months, and drinking risk at 3 months.

Because rates of unintended pregnancy and binge drinking that create AEP risk are inequitable between Native women and the general population, CARRII must be tailored to and optimized for this priority subgroup. Guided by the Multiphase Optimization Strategy (MOST), we will tailor CARRII's existing components for Native women and systematically test proposed novel components (derived from formative work with Native women), to develop an efficient and scalable intervention tailored to Native women at risk of AEP. Optimizing CARRII for Native women will require measuring the efficacy and costs of components to find a balance between impact and affordability for Native communities. The goal is to determine the optimal combination of novel intervention strategies to include with CARRII (tailored for Native women) that maximizes digital intervention efficacy at feasible cost for Native communities.

**What will participants do in this study?** Please provide an overall summary of the study plan. Where and when it will be conducted? What do you hope to learn from these activities? If the study has more than one phase, clearly map out the different phases. You will be required to describe the study components in more detail in later sections but use this paragraph to help your IRB reviewer to understand the general outline of the study. Other sections in the protocol form can be seen below.

For Aim 1 there are four study methods that will help the team evaluate and tailor CARRII intervention components for Native women and prepare for a trial. These iterative mixed methods formative studies include: a) develop an ongoing Native Partners Working Group to review study plans and findings over time with the research team, b) Quantitative surveys to estimate rate of AEP risk, interest/ ability to participate, health literacy, and other factors (n=300), c) Focus Groups to prototype and tailor new CARRII components (n=60), and d) Think-aloud User Testing (n=20) to finalize the CARRII intervention. The tailored CARRII core and its new components will be developed on a responsive design platform to permit use on any device.

Mixed methods research during Aim 1 will include 4 different components. They are: 1. Convene working group of Native American stakeholders. This will include indigenous women from the Southwestern region, urban Denver and the Mountain West region, where consultant [name] is located and conducts Native health studies, and the Great Plains regions of Minnesota, South Dakota, and North Dakota where University of Minnesota-Duluth partner researcher [name] is located and routinely recruits for her research. Indigenous women from the Mid-Atlantic may also be recruited, as UVA's indigenous representative, [name], is connected to several tribes and groups of Native Americans residing in this region.

2. Collect data using a 35-minute survey of demographics, AEP risk, device use, recommendations for recruitment methods, and interest in subsequent trial with 300 Native women respondents, targeting approximately 100-150 per region (rural Great Northern Plains), urban Denver and rural mountain West and Southwest.

3. Conduct Iterative prototyping of existing and proposed CARRII components with 60 Native women across 10 Focus Group discussions. Content will be informed by Components 1 and 2.

4. Conduct User Testing of existing CARRII and candidate components with Think-Aloud methods among 20 Native women.

In Aim 2, we will Pilot test 5 new candidate components tailored to Native women at risk of AEP: After incorporating input from participants (SA 1) and the Native Partners Working Group, we will pilot candidate components to assess independent effects on AEP behavioral risk factors (drinking and contraception) while considering practical aspects such as frequency and duration of contact with participants, and costs of each component.

Participants will be Native women aged 18-44 with some drinking and some risk for pregnancy (some ineffective contraception use). Participants must have access to the Internet via a device they can access at least weekly. Each participant will complete a baseline survey including a telephone-administered 30-day Timeline follow-back of alcohol use and contraception use, to determine eligibility, and a short online survey evaluating knowledge about AEP risk, intentions and self-efficacy to change, and readiness to change alcohol and/or contraception behaviors.

They will then be randomized to receive one novel component condition, each of which is designed as an engaging experience that boosts motivation to continue participating, for a 6-week period. All participants will complete the 4 Cores of the CARRII Native internet intervention over the 6-week period alongside the novel component.

The candidates that will be tested are: 1) Telephone-administered 30-day timeline follow-back (TLFB) of drinking, sex, and contraception, administered by phone, of alcohol intake and contraception type by sexual encounter at enrollment and monthly (2 weeks after enrollment), which should increase awareness of AEP risk and motivation for alcohol and contraception behavior change, 2) Mailed pregnancy tests sent monthly to raise consciousness of pregnancy risk and to detect a new pregnancy early, which should increase motivation for contraception behavior change, 3) Automated, personalized digital safer sex and drink counting/reduction skills training, to improve drinking self-management skills and self-efficacy for drinking reduction and contraception use, 4) Fully automated text messaging prompting usage of safer sex and drink reduction skills, to prompt behavior change, which should increase self-efficacy for behavior change, and 5) Access to an anonymized Community Message Board of Native women to discuss challenges in behavior change, to give and receive social support, which should increase perceived social support for behavior change.

We plan interim phone calls after 3 weeks in the pilot trial to check on progress.

Participants will complete a second TLFB for the past 6 weeks for drinking and contraception behavior, and a short survey to rate the component they experienced, along with the System Usability Scale on their component, and measures of short-term knowledge, intentions to change, self-efficacy for change, and readiness to change alcohol use and contraception behaviors.

This Aim will determine preliminary effect sizes on alcohol and contraception use and costs of each new component. New components with the highest effect sizes in the 6-week pilot trials will be integrated with the tailored CARRII core intervention.

**Is this study topic relevant to cancer risk factors, prevention, cancer treatment, or survivorship (e.g., pain, financial toxicity, etc.), or will the study purposefully include participants currently or previously diagnosed with cancer, or their caregivers?**

No

**(optional) Study Overview file upload:** Below you have the option to upload additional files to help the Board better understand your study. You are not required to provide any additional explanation beyond completing the text boxes provided in this Study Overview section; however, for example, if you are using a new technology or a complicated process that would be more easily demonstrated with an image or video, you can upload the file here.

Study Overview

View File: [contra\\_card\\_shortened\\_20240730.pdf](#)

date uploaded: 2024-10-31, by: [name] (spp2d)

*This file is approved.*

date approved: 2024-11-08

Study Overview

View File: [drink\\_card\\_illustration\\_20240813.pdf](#)

date uploaded: 2024-10-31, by: [name] (spp2d)

*This file is approved.*

date approved: 2024-11-08

Study Overview

View File: [HSR220448 LOS Missouri Breaks.pdf](#)

date uploaded: 2024-09-04, by: [name] (spp2d)

*This file is approved.*

date approved: 2024-09-18

Study Overview

View File: [SBS6760 Aim 2 CARRII Native push notifications.pdf](#)

date uploaded: 2024-08-20, by: [name] (spp2d)

*This file is approved.*

date approved: 2024-09-18

Study Overview

View File: [SBS6760 Aim 2 CARRII Native Women Anonymous CMB Agreement 08.01.2024.docx](#)

date uploaded: 2024-08-20, by: [name] (spp2d)

*This file is approved.*

date approved: 2024-09-18

Study Overview

View File: [SBS6760 Aim 2 How to Use a Pregnancy Test.docx](#)

date uploaded: 2024-08-20, by: [name] (spp2d)

*This file is approved.*

date approved: 2024-09-18

Study Overview

View File: [SBS6760 Aim 2 Novel Component CMB\\_\(1\).docx](#)

date uploaded: 2024-08-21, by: [name] (spp2d)

*This file is approved.*

date approved: 2024-09-18

Study Overview

View File: [SBS6760 Aim 2 Novel Component Digital Skills.docx](#)

date uploaded: 2024-08-20, by: [name] (spp2d)

*This file is approved.*

date approved: 2024-09-18

Study Overview

View File: [SBS6760 CARRII Native logos 11.04.24.docx](#)

date uploaded: 2024-11-06, by: [name] (spp2d)

*This file is approved.*

date approved: 2024-11-08

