**Describe this Data Source.**

Each participant, after consenting, will complete a demographics questionnaire online via Qualtrics, and then be interviewed by the coordinator, to complete a 30-day TLFB to determine eligibility. This will include the following instruments:

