**Describe the processes for linking the data:**

Aim 1 prescreening data will be matched with Survey data and combined based on Study ID number.

In Aim 2, each participant will complete:

--a telephone-administered 30-day month Timeline follow-back of alcohol use and contraception use, and 2 baseline surveys including:

--a short online survey evaluating knowledge about AEP risk, intentions and self-efficacy to change, and  
--readiness to change alcohol and/or contraception behaviors.

All Aim 2 participants will also complete:

--a second TLFB for the past 6 weeks for drinking and contraception behavior, and  
--a short survey to rate the component they experienced, along with  
--the System Usability Scale on their component, and  
--repeat the 2 baseline surveys.

Aim 2 participants who are randomized to the 30-day TLFB component will complete an additional telephone-administered past month Timeline follow-back four weeks after enrollment.

Data will be recorded by primary unique Study ID number.

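### All five Aim 2 arms receive the enrolment TLFB that is part of component 1, so arm 1 can estimate only the increment of one added call, whose date the protocol gives in two ways

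*Combined protocol and SAP*

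**What the plan says.** The Study Overview lists five candidate components, and each participant is randomised to one of them alongside the four CARRII Native Cores. Component 1 is a TLFB "administered by phone, of alcohol intake and contraception type by sexual encounter at enrollment and monthly (2 weeks after enrollment". The interview is offered as an active ingredient, "which should increase awareness of AEP risk and motivation for alcohol and contraception behavior change".

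The same interview is also the eligibility assessment for everyone. The Study Overview says: "Each participant will complete a baseline survey including a telephone-administered 30-day Timeline follow-back of alcohol use and contraception use, to determine eligibility". Under Data Sources, the entry on Aim 2 demographics and the eligibility TLFB says each participant will "be interviewed by the coordinator, to complete a 30-day TLFB to determine eligibility".

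The section on associating data sources, where it describes the linking process, states what sets arm 1 apart: those randomised to the TLFB component "will complete an additional telephone-administered past month Timeline follow-back four weeks after enrollment". It also gives the outcome interview for all arms: "a second TLFB for the past 6 weeks for drinking and contraception behavior".

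The results drive a selection. The Study Overview says: "New components with the highest effect sizes in the 6-week pilot trials will be integrated with the tailored CARRII core intervention". The Aim 2 analysis text under Data Reports & Storage names baseline to 6-week change on the TLFB as the primary outcome. It uses the component effect sizes both to choose what enters the Aim 3 factorial experiment and to power it.

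**The concern.** A component's effect can be isolated only if some arm goes without it. Half of component 1, the enrolment interview, is given to all five arms. If that interview changes behaviour as the protocol expects, it raises the baseline to 6-week change everywhere, and arm 1 gets no relative credit for it. A core-only arm would not solve this, since its members would also take the eligibility TLFB.

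The one call that does distinguish arm 1 comes partway through the original 6-week period. Part of the outcome window therefore precedes it, by an amount that depends on which section is right about the date. The call also asks arm 1, and no other arm, about days that the final TLFB covers again, so outcome measurement is not identical across arms.

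The risk is that the TLFB component is set aside, or Aim 3 is powered, on a figure taken to describe the whole component when it describes one added interview.

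**Working it through.** The documents give no power, alpha or assumed effect for Aim 2, so there is no plan figure to reproduce. The check counts sessions and days.

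**Inputs.** Enrolment TLFB in all arms (Study Overview; Data Sources; linking text). Added call in arm 1 only, at day 14 (Study Overview) or day 28 (linking text), with 30-day recall. Outcome window of 6 weeks, 42 days. An extension of 16 days after the Qualtrics outage (Unexpected Adverse Events), giving 42 + 16 = 58 days. Aim 2 sample of 53, including up to 3 test users (Recruitment & Consent).

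**Sessions before the outcome interview.** Arm 1: two. Every other arm: one. Difference: one call.

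**Days.**

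| | Call at day 14 | Call at day 28 |
|---|---|---|
| Original window, days after the call | 42 − 14 = 28 (67%) | 42 − 28 = 14 (33%) |
| Original window, days asked about twice, arm 1 only | 14 | 28 |
| Extended, all 58 days counted, share after the call | 44/58 = 76% | 30/58 = 52% |
| Extended, last 42 days counted, share after the call | 42/42 = 100% | 30/42 = 71% |
| Extended, last 42 days counted, days asked about twice | 0 | 12 |

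The documents do not say which window the final TLFB covers once the period is extended.

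**Share of the component's effect in the contrast.** Assume each session has the same effect e per day, starting at once and lasting. Over the original 42 days:

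- Component as delivered in arm 1: e × (42 + 28)/42 with a day-14 call, or e × (42 + 14)/42 with a day-28 call.
- Arm 1 minus another arm, TLFB part only: e × 28/42 or e × 14/42.
- Ratio: 28/70 = 40% or 14/56 = 25%.

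**Consequence for the ranking.** With about (53 − 3)/5 = 10 per arm (equal allocation assumed; no ratio is given) and an SD of change of 1, each arm mean has SE 1/√10 = 0.32, and a difference between two arms has SE √(2/10) = 0.45. A simulation of 400,000 pilots gave the other four arms a true effect d and the TLFB arm f × d. Here f = 2/3 or 1/3 represents an added call as strong as the other components, but only on the days after it. With equal true effects, an arm is last 20% of the time and in the top two 40%.

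| d | TLFB arm last, f = 2/3 / 1/3 | TLFB arm in top two, f = 2/3 / 1/3 |
|---|---|---|
| 0.2 | 25% / 31% | 33% / 27% |
| 0.5 | 34% / 51% | 24% / 12% |
| 0.8 | 44% / 71% | 17% / 4% |

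The values of d are assumed, since the protocol states that the effect sizes are unknown.

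**The case against.** The planned measure is change within each arm, and arm 1's change includes both TLFBs. A reader might infer that the component cannot be measured at all. The documents do not support that: the increment of one added call over the shared interview can be estimated, though imprecisely. The shared interview raises all arms alike, so what arm 1 loses is relative advantage.

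A reader might also infer that the component must rank low whether or not it works. That does not follow either. If the added call is as strong over the whole window as the other components are, there is no penalty, and even under the dilution assumed above the TLFB arm reaches the top two in 4% to 33% of simulated pilots.

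Two more points stand. All components are delivered during the same six weeks, and the mailed pregnancy tests are also monthly, so intermittent delivery is not unique to arm 1. What is unique is that its first dose is shared with every comparator. And under the extension, a day-14 call can fall before the last 42 days, so the call need not lie inside the outcome window for every participant.

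Finally, the protocol calls these effect sizes preliminary, and with about 10 per arm sampling error limits all five estimates. That lowers the practical weight of the point, but a larger sample would not remove it. The direction of any bias from asking arm 1 twice about the same days is not established.

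**Conclusion.** The point holds in a limited form. Aim 2 cannot isolate the effect of component 1 as the Study Overview defines it. It can estimate one added TLFB on top of the interviews everyone receives. That is settled by the protocol's own text and needs no assumption.

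The size does rest on assumptions. With equal, immediate and lasting session effects on the original schedule, the contrast holds about 25% to 40% of the component's effect as delivered, and the ranking is tilted against it to a degree that depends on the true effects. Dividing instead by two sessions acting on all 42 days would give about 17% to 33% (0.5 × 0.33 to 0.5 × 0.67), but no participant has that exposure. For extended participants the exposed share is higher and cannot be fixed until the window is stated.

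The two call dates contradict each other, and the choice between them doubles or halves the exposed share on the original schedule. The documents do not justify striking the component from the ranking. They do require that its rank be read for what it measures.

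**What to change.** 1. In the Study Overview and the Aim 2 analysis text under Data Reports & Storage, state that arm 1 estimates the effect of one added mid-pilot TLFB over the TLFBs all arms receive. Carry that meaning into the ranking and the Aim 3 power inputs, and say that a low rank is not evidence that the TLFB component does not work.
2. Reconcile the date of the added call between the Study Overview and the linking text.
3. As a supplementary analysis in all arms, calculate the drinking and contraception outcomes from the final-TLFB days after the reconciled call date. On the original schedule these are also days that arm 1 has not been asked about before.

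Steps 1 and 2 cost only wording. Step 3 needs no new participants, visits or arms, provided the TLFB data are kept by day. It uses only 28 or 14 of the original 42 days, so the estimate is noisier. It does not recover the effect of the shared enrolment interview.

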## Participant Groups

**Participant Group Name:** Aim 1 Survey participants

**Age Range (years):** 18-44

**Vulnerable populations:** no vulnerable population (none)

**Maximum number of participants, in this group, expected to enroll over the life of the study:** 300

**Minimum number of participants, in this group, expected to enroll over the life of the study:** 1

**Total number of participants, in this group, ever enrolled:** 0

**Approximate number of participants, in this group, currently enrolled:** 0

**Future Enrollment:** We will enroll participants, in this group, during the next twelve months

**Approximate number of participants, in this group, expected to enroll in the next twelve months:** 300

**Have participants, in this group, withdrawn from the study in the past year?** No

**Describe the participants in this group.**

Inclusion Criteria: participants must be between 18 and 44 years of age, sex assigned female at birth, and self-identify as Native American women.

Because rates of unintended pregnancy and binge drinking that create AEP risk are inequitable between Native women and the general population, CARRII must be tailored to and optimized for this priority subgroup.

**Will participants in this group be compensated for taking part in your study?** Yes

**Are any of the participants US citizens or US residents?** Yes

This question applies only to participants who are US citizens or US residents.

**Will participant payments be processed through an account administered by UVA?** No

**Describe your payment process, including information about the amount participants will be paid and how payment will be issued and delivered to participants.**

Participants will be paid \$20 by e-gift card for survey completion.

**Participant Group Name:** Aim 2 Pilot Testing

**Age Range (years):** 18-44

**Vulnerable populations:** no vulnerable population (none)

**Maximum number of participants, in this group, expected to enroll over the life of the study:** 53

**Minimum number of participants, in this group, expected to enroll over the life of the study:** 1

**Total number of participants, in this group, ever enrolled:** 0

**Approximate number of participants, in this group, currently enrolled:** 0

**Future Enrollment:** We will enroll participants, in this group, during the next twelve months

**Approximate number of participants, in this group, expected to enroll in the next twelve months:** 53

**Have participants, in this group, withdrawn from the study in the past year?** No

